## 1.2 PRIOR RESEARCH

### 1.2.1 Experimental Vaccines against RSV

Efforts have been directed toward the development of a live-attenuated RSV vaccine because of the advantages of live-attenuated vaccines over inactivated or subunit vaccines. These advantages include the ability to (i) induce the full spectrum of protective immune responses including serum and local antibodies as well as CD4+ and CD8+ T cells and innate immunity; (ii) infect and replicate in the presence of maternal antibody, permitting immunization of young infants; and (iii) produce an acute, self-limited, attenuated infection that is well tolerated and readily eliminated from the respiratory tract. Another important advantage is the absence of vaccine-related enhanced disease, as has been confirmed in clinical studies (10).

Several live-attenuated RSV vaccines have been evaluated in clinical trials in adult and pediatric populations as part of NIAID's ongoing RSV vaccine development program (11, 23-26). Four vaccine viruses with the NS2 deletion have been evaluated in clinical studies: rA2cpΔNS2, rA2cp248/404ΔNS2, rA2cp530/1009ΔNS2 (27), and RSV ΔNS2/Δ1313/I1314L. A brief summary of clinical studies involving these vaccine candidates is provided below.

## RSV Vaccine Candidates with an NS2 Deletion

rA2cp $\Delta$ NS2 contains the NS2 deletion as well as a set of 5 amino acid substitutions in the N, F, and L proteins that were identified in a cold-passaged (cp) RSV (V267I in N; E218A and T523I in F; and C319Y and H1690Y in L) (28, 29). rA2cp248/404 $\Delta$ NS2 contains all of the mutations in rA2cp $\Delta$ NS2 as well as two additional point mutations: "248," an amino acid substitution in the L protein (Q831L) (28, 30, 31), and "404," a nucleotide substitution in the M2 gene start signal (30, 32). rA2cp530/1009 $\Delta$ NS2 also contains all of the mutations in rA2cp $\Delta$ NS2 as well as two additional point mutations in L: "530" (F521L) and "1009" (M1169V) (33, 34).

rA2cp $\Delta$ NS2, which had the fewest attenuating mutations, was evaluated in a dose-escalating study ( $10^{5.0}$  PFU,  $10^{6.0}$  PFU, or  $10^{7.0}$  PFU) administered to a total of 45 adults, and was also evaluated at a dose of  $10^{5.0}$  PFU in eight 15- to 59-month-old RSV-seropositive children. Shedding of rA2cp $\Delta$ NS2 was not detected in any of the adults, and only 2 of 16 adults who received  $10^{7.0}$  PFU had an antibody response. In contrast, at the dose of  $10^{5.0}$  PFU, rA2cp $\Delta$ NS2 was shed by 3 of 8 vaccinated seropositive children with mean peak titers of  $10^{3.4}$  PFU/mL of nasal wash. Two additional children had detectable virus by polymerase chain reaction (PCR). Based on these results, rA2cp $\Delta$ NS2 was deemed under-attenuated, and was not further evaluated in seronegative children.

rA2cp248/404 $\Delta$ NS2 was evaluated in adults (n = 16 vaccinees), 15- to 59-month-old RSV-seropositive children (n = 16 vaccinees), and 6- to 24-month-old RSV-seronegative children (n = 10 vaccinees). rA2cp248/404 $\Delta$ NS2 was not shed by adults. Only one seropositive child shed vaccine virus (peak titer of  $10^{0.4}$  PFU/mL of nasal wash), and four seronegative children shed vaccine virus (mean peak titer of  $10^{2.3}$  PFU/mL of nasal wash).

rA2cp530/1009 $\Delta$ NS2 was also evaluated in adults (n = 19 vaccinees), 15- to 59-month-old RSV-seropositive children (n = 14 vaccinees), and 6- to 24-month-old RSV-seronegative children (n = 15 vaccinees). rA2cp530/1009 $\Delta$ NS2 was shed by one adult (peak titer of  $10^{0.4}$  PFU/mL of nasal wash), none of the seropositive children, and three seronegative children (mean peak titer of  $10^{1.3}$  PFU/mL of nasal wash). In summary, deletion of the NS2 gene attenuates RSV. rA2cp $\Delta$ NS2 was over-attenuated for adults but under-attenuated for young children, whereas both rA2cp248/404 $\Delta$ NS2 and rA2cp530/1009 $\Delta$ NS2 were over-attenuated and insufficiently immunogenic for seronegative children (27).

Based on these results, RSV $\Delta$ NS2/ $\Delta$ 1313/I1314L was developed. In a recent phase I trial (NCT01893554), this candidate vaccine was evaluated in RSV-seropositive children 12-59 months of age at a dose of  $10^6$  PFU (10V, 5P), and no shedding or immune response was detected, indicative of attenuation. Next, it was evaluated in seronegative children 6-24 months of age at two sequential dose levels. At the lower dose of  $10^5$  PFU (15V, 7P), the vaccine was poorly infectious and immunogenic: 7% of recipients shed virus detected by culture, and 53% developed a RSV neutralizing antibody responses. At the higher dose of  $10^6$  PFU (20V, 10P), 80% of recipients shed virus detected by culture, and 80% developed a RSV neutralizing antibody response.

To generate a vaccine candidate with a slightly increased level of replication compared to RSV  $\Delta$ NS2/ $\Delta$ 1313/I1314L, the current candidate vaccine RSV 6120/ $\Delta$ NS2/1030s was designed. RSV 6120/ $\Delta$ NS2/1030s is expected to be slightly less restricted in replication than RSV $\Delta$ NS2/ $\Delta$ 1313/I1314L, and more immunogenic in RSV-seronegative infants and children.

## 1.2.2 Preclinical Studies

### 1.2.2.1 Temperature sensitivity of RSV 6120/ΔNS2/1030s

The shutoff temperature ( $T_{SH}$ ) was evaluated by efficiency of plaque formation at temperatures indicated in Table 2. RSV 6120/ΔNS2/1030s is moderately temperature sensitive, with a  $T_{SH}$  of 40°C. The  $T_{SH}$  is defined as the lowest restrictive temperature at which the reduction in plaque number compared to that at the permissive temperature of 32°C is 100-fold or greater than that observed for wt RSV at the 2 temperatures. Small plaques were observed at 38°C, and plaques formed at 39°C and above were characterized as micro-plaques. Temperature sensitivity results of the vaccine candidate RSV ΔNS2/Δ1313/I1314L were included for comparison (Table 2). As expected, the temperature sensitivity of RSV ΔNS2/Δ1313/I1314L was slightly greater than that of RSV 6120/ΔNS2/1030s ( $T_{SH}$  of 39°C, small plaque temperature [ $T_{SP}$ ] of 37°C for RSV ΔNS2/Δ1313/I1314L;  $T_{SH}$  of 40°C,  $T_{SP}$  of 38°C for RSV 6120/ΔNS2/1030s).

**Table 2: Temperature Sensitivity of Experimental Lots of RSV 6120/ΔNS2/1030s and RSV ΔNS2/Δ1313/I1314L**

Virus	Virus titer ( $\log_{10}$ PFU per mL) at indicated temperature (°C) a									
	Repl b	32	35	36	37	38	39	40	$T_{SH}$ c	$T_{SP}$ d
wt RSV	1	8.0	8.0	7.9	7.9	7.8	7.6	7.5	> 40	> 40
wt RSV	2	6.7	6.9	6.8	6.8	6.9	6.8	6.6	> 40	> 40
RSV ΔNS2 Δ1313 I1314L	1	7.5	7.3	7.0	6.7	5.7	1.7	< 1	39	37
RSV 6120/ΔNS2/1030s	2	7.8	7.9	7.9	7.7	7.8	7.5 e	5.5e	40	38

a The temperature sensitivity (ts) phenotype for each virus was evaluated by plaque assay on Vero cells at the indicated temperatures. For viruses with ts phenotype, titers at shutoff temperatures are marked (bold, underlined). Vero cells were used for the ΔNS2 viruses because loss of expression of NS2 renders RSV more sensitive to type I interferon, which is not made by Vero cells. See footnote c for the definition of shutoff temperature.

b wt RSV rows 1 and 2 represent duplicate dilution series of the same virus that were examined in parallel in the same experiment. Differences between these replicas illustrate the variability that is inherent in these biological experiments.

c Shutoff temperature ( $T_{SH}$ , bold, underlined) is defined as the lowest restrictive temperature at which the reduction compared to 32°C is 100-fold or greater than that observed for wt RSV at the two temperatures. The ts phenotype is defined as having a shutoff temperature of 40°C or less.

d  $T_{SP}$ , small plaque temperature, is defined as the lowest restrictive temperature at which the small-plaque phenotype is observed.

e At 39 and 40°C, RSV 6120/ΔNS2/1030s formed micro-plaques.

[figure not shown]
### 1.2.2.2 Replication of an experimental lot of RSV 6120/ΔNS2/1030s in an in-vitro model of mucociliary normal human tracheal/bronchial epithelial cells

Multicycle growth of an experimental lot of RSV 6120/ΔNS2/1030s was evaluated in a 3D mucociliary human tissue model consisting of normal differentiated primary human tracheal/bronchial airway epithelial cells (EpiAirway, Mattek, Inc.). Virus replication was evaluated at two different temperatures (32°C and 37°C) to model the temperatures of the upper and lower airways. Pseudostratified differentiated airway cells were cultured in an air-liquid interface in 12-mm transwell inserts with 0.4  $\mu$ M pore sizes in Dulbecco's Modified Eagle Medium (DMEM), supplemented with a proprietary mix of epidermal growth factors and other proprietary factors. Prior to infection, the apical surfaces of the cultures were washed with 500  $\mu$ L

PBS to remove any accumulated mucus. Triplicate wells were infected at a multiplicity of infection of 0.1 with 100  $\mu$ L per well of RSV 6120/ΔNS2/1030s. To evaluate replication at 32°C, recombinant wt RSV A2 and RSV ΔNS2/Δ1313/I1314L were included for comparison. At 37°C, only recombinant wt RSV was included for comparison. After 2 hours of adsorption, the inoculum was gently removed, and the apical surfaces of the cultures were washed 3 times with 300  $\mu$ L PBS. Apical washes were collected daily on days 1-7 post-infection to assay viral replication, then snap-frozen, and virus titers were determined by immunoplaque assay on Vero cells.

Recombinant wt RSV of strain A2 replicated efficiently in differentiated primary human tracheal/bronchial epithelial cells at 32°C and at 37°C (Figure 3). At 32°C, peak titers of wt RSV were detectable on day 6, whereas at 37°C, peak titers were reached by day 5 post-infection. The temperature-sensitive virus RSV ΔNS2/Δ1313/I1314L, which differs from RSV 6120/ΔNS2/1030s only by the attenuating mutation in the L ORF, was included for comparison at the lower temperature, 32°C. Peak titers of this virus were about 200-fold lower than those of wt RSV at 32°C. RSV 6120/ΔNS2/1030s replicated to slightly higher titers than RSV ΔNS2/Δ1313/I1314L, showing that indeed, RSV ΔNS2 with the 1030s mutation is slightly less restricted for replication than RSV ΔNS2 with the genetically stabilized deletion of codon 1313 of the L ORF. At 37°C, the difference in peak titers between RSV 6120/ΔNS2/1030s and wt RSV was statistically significant.

**Figure 3: Multicycle Replication of Experimental Lots in an in-vitro Model of Normal Human Bronchial/Tracheal Epithelial Cells**

Cultures were infected at a multiplicity of infection of 0.1, and supernatants were harvested daily for 7 days, snap-frozen, and titrated later on Vero cells. A: replication at 32°C. B: replication at 37°C.

### **1.2.2.3 Replication of experimental lot and CTM of RSV 6120/ΔNS2/1030s in African green monkeys (AGMs)**

Replication and immunogenicity of RSV 6120/ΔNS2/1030s were evaluated in nonhuman primates (NHPs), specifically African green monkeys (AGM). AGMs are semi-permissive for RSV. The first NHP study was done in AGMs to evaluate an experimental lot of RSV 6120/ΔNS2/1030s, and a second study was done to evaluate the CTM (Lot RSV#012A). AGMs that were seronegative for RSV were inoculated intranasally (i.n.) and intratracheally (i.t.) with RSV 6120/ΔNS2/1030s; a dose of  $1 \times 10^6$  PFU of vaccine in a 1-mL volume per site was administered to sedated juvenile male and female AGMs (total dose per animal:  $2 \times 10^6$  PFU). Nasopharyngeal swabs were collected daily on days 0 through 10 and on days 12 and 14; tracheal lavage (TL) samples were collected every other day from days 2 through 14; and virus shedding was analyzed by immunoplaque assay. Serum RSV neutralizing antibody titers were determined by a complement-enhanced 60% plaque reduction neutralization assay. Results from studies following the same protocol, performed in animals from the same group and origin, inoculated with recombinant wtRSV A2 at the same dose, were included for comparison. Studies were approved by the Animal Care and Use Committee of NIAID, NIH.

In both studies, shedding of the RSV 6120/ΔNS2/1030s virus from the upper respiratory tract (URT) and lower respiratory tract (LRT) was detectable over several days. In both studies, the mean peak titers of RSV 6120/ΔNS2/1030s in the nasopharyngeal samples was  $3.8 \log_{10}$  PFU per mL. These mean peak titers were slightly lower than that of wt RSV A2 ( $4.2 \log_{10}$  PFU per mL), but higher than those of the previously tested RSV ΔNS2/Δ1313/I1314L virus ( $3.2 \log_{10}$  PFU per mL). The mean peak titers in the LRT, detectable in TL samples, were  $4.6 \log_{10}$  PFU per mL for the Experimental Lot of RSV 6120/ΔNS2/1030s, and  $2.9 \log_{10}$  PFU per mL for the CTM of RSV 6120/ΔNS2/1030s. Shedding was observed in all AGMs in both URT and LRT. Compared to the RSV ΔNS2/Δ1313/I1314L virus, which showed much lower mean peak titers ( $1.4 \log_{10}$  PFU per mL) with only a 75% infection rate (virus replication detected in 3 out of 4 animals), the study virus RSV 6120/ΔNS2/1030s was less attenuated in the AGMs (Appendix I, Table 27, Table 28).

In both studies, the RSV 6120/ΔNS2/1030s virus induced serum neutralizing antibodies. In the first study of the experimental lot, the neutralizing antibody titers were comparable to or slightly higher than wt RSV A2 and the previously tested RSV vaccine virus (RSV ΔNS2/Δ1313/I1314L) (Appendix I, Table 29). The CTM induced titers that were slightly lower than those of wt RSV, and comparable to those of RSV ΔNS2/Δ1313/I1314L. These results show that at a total dose of  $2 \times 10^6$  PFU, administered i.n. and i.t., RSV 6120/ΔNS2/1030s is immunogenic in AGMs.

### **1.2.3 Previous Clinical Experience**

The live-attenuated recombinant RSV 6120/ΔNS2/1030s vaccine virus is being evaluated for the first time in humans. Based on preclinical data, RSV 6120/ΔNS2/1030s is expected to be more attenuated than the previously tested vaccine candidate rA2cpΔNS2, but less attenuated than the vaccine candidates rA2cp248/404ΔNS2 and rA2cp530/1009ΔNS2, which were deemed over-attenuated in seronegative infants and children, and slightly less attenuated and more immunogenic than RSVΔNS2/Δ1313/I1314L. As noted above, this vaccine is predicted to be attenuated and well tolerated in seropositive and seronegative children.

## **1.3 RATIONALE**

## **1.4 CLINICAL DEVELOPMENT PLAN**

The investigational RSV vaccine RSV 6120/ΔNS2/1030s will be evaluated sequentially in RSV-seropositive children followed by evaluation in RSV-seronegative infants and children. The main purpose of this study is to determine whether RSV 6120/ΔNS2/1030s is well tolerated and restricted in replication in RSV-seropositive children, and well tolerated, infectious, immunogenic, and genetically stable in RSV-seronegative infants and children. If the study product is found to be well tolerated, infectious, and immunogenic in RSV-seronegative infants and children, then a safety and immunogenicity study in infants < 6 months of age will be initiated. Plans will be made in consultation with industry collaborators as a lead RSV vaccine candidate is identified.

The primary immunogenicity endpoints to be evaluated are RSV neutralizing antibody titer, and RSV F protein antibody (by ELISA). Neutralizing antibody is a well-established and important surrogate marker of effective immunity to RSV disease. Antibodies to the F protein are also associated with cross-subgroup neutralization and protection (13). These assays will be performed at the Johns Hopkins University (JHU) CIR laboratory.

## **1.5 HYPOTHESES**

RSV 6120/ΔNS2/1030s will be well-tolerated in RSV-seropositive and RSV-naïve participants. In RSV-seronegative participants, RSV 6120/ΔNS2/1030s is expected to be safe and result in infection, limited vaccine replication, and the induction of a neutralizing antibody response to RSV.

# **2 OBJECTIVES**

## **2.1 PRIMARY OBJECTIVES**

### *Safety*

1. To assess the frequency and severity of study product-related solicited and unsolicited AEs in RSV-seropositive participants (group 1) from day 0 through the 10th day following inoculation
2. To assess the frequency and severity of study product-related solicited and unsolicited AEs in RSV-seronegative participants (group 2) from day 0 through the 28th day following inoculation
3. To assess study product-related serious adverse events (SAEs) in RSV-seropositive participants (group 1) from day 0 through the 28th day following inoculation
4. To assess study product-related SAEs in RSV-seronegative participants (group 2) from day 0 through the 56th day following inoculation

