**Table 1: Inoculation Schedule**

Group #	N	Study Product	Dose
1	10	RSV 6120/ΔNS2/1030s	$10^{5.7}$ PFU*
	5	Placebo	0
2	14-20	RSV 6120/ΔNS2/1030s	$10^{5.0}$ PFU*
	7-10	Placebo	0

\*plaque-forming units (PFU)

[figure not shown]
The study will start with group 1 and proceed to group 2 if there are not more than 2 vaccine-associated solicited adverse events (AEs) (Days 0 through 10) and no vaccine-associated lower respiratory illnesses (LRIs) (Days 0 through 28) in RSV-seropositive children. If 3 or more RSV-seropositive children (group 1) have respiratory or febrile illness that coincides with shedding of  $> 10^{2.5}$  PFU of vaccine virus as detected by culture, then we will evaluate the safety, infectivity, and immunogenicity of the vaccine virus in an additional 15 RSV-seropositive children before determining whether to continue with group 2.

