## **3 STUDY DESIGN**

The study will be double-blind, randomized, and placebo-controlled. Participants in groups 1 and 2 will be block-randomized in groups of 3 at a ratio of 2:1 to receive vaccine or placebo, respectively. The vaccine will be evaluated in a stepwise fashion beginning with RSV-seropositive children (Group 1) and proceeding sequentially in RSV-seronegative children (Group 2). For the purpose of this study, RSV-seropositive is defined as having a serum neutralizing antibody titer of  $\geq 1:40$ , and RSV-seronegative is defined as having a serum neutralizing antibody titer of  $< 1:40$ . This definition has been used in previous evaluations of live-attenuated RSV vaccines (11, 24, 35). In these previous studies, live-attenuated RSV vaccines were highly restricted in replication and poorly immunogenic in children with titers  $\geq 1:40$  but were far less restricted in replication and highly immunogenic in children with titers  $< 1:40$ . These data suggest that this neutralizing antibody cutoff can distinguish effectively between RSV-experienced and RSV-naïve children.

The study will proceed to group 2 if there are not more than 2 vaccine-associated solicited AEs and no vaccine-associated LRIs in RSV-seropositive children. If 3 or more RSV-seropositive children have respiratory or febrile illness that coincides with shedding of  $> 10^{2.5}$  PFU of vaccine virus as detected by culture, then we will enroll an additional 15 RSV-seropositive children to continue evaluating the safety, infectivity, and immunogenicity of the vaccine virus.

Enrollment occurs at the time of inoculation with study product, Day 0, and will occur between April 1 and October 31 to avoid the time during which wt RSV typically circulates in the community ([Appendix V](#), Figure 6). Accrual will stop prior to November 1.

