**Table 19: AE CRF Recording Requirements for RSV-Seropositive Subjects**

Study Phase at the Time of Event Onset	Calendar Date	AEs to Record on CRFs	Concomitant Medications to Record on CRFs
Day 0 through midnight of 10 th day following inoculation (Acute Phase)	ANY	
 
• All SAEs
 
• All solicited AEs that meet Appendix IV, criteria
 
• All unsolicited AEs (Grades 1 to 4), with the exception of the following conditions if not treated with prescription medication or non-prescription medications with antipyretic properties: diaper rashes, teething pain, and spitting up
 
	
Record these medications on the CRFs regardless of whether the related event is recorded on the CRFs:
 
 
• All cough and cold remedies including decongestants, cough suppressants, expectorants
 
• All nasal sprays (except saline spray)
 
• All antihistamines
 
• All antipyretics
 
• All prescription medications
 
 
For SAEs and LRIs:
 
 
• All medications related to the recorded event
 

From the 11 th day after inoculation to the 28 th day after inoculation (Post-Acute Phase)	ANY	
 
• All LRIs and SAEs
 
	
 
• All medications related to the recorded event
 

Throughout study	ANY	
 
• Unresolved AEs or SAEs with onset from Day 0 to midnight on the 10th day after inoculation
 
• Unresolved LRIs and SAEs with onset prior to the 28th day following inoculation
 
• 
 
	
 
• All medications related to the recorded event
 

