### 7.3 SERIOUS ADVERSE EVENT REPORTING

All SAEs will be reviewed by a study physician, recorded on the Safety Expedited Report Form (SERF) and followed through to resolution. SAEs that have not resolved by the end of the follow-up period are followed until final outcome is known. If it is not possible to obtain a final outcome for an SAE (e.g., the subject is lost to follow-up), the reason a final outcome could not be obtained will be recorded by the investigator on the AE CRF and the SERF. In addition to the SAE Reporting Category identified below, other AEs that must be reported in an expedited manner are LRIs as defined in Appendix IV if they occur during study days 0 to 10 in groups 1 and study days 0 to 28 in group 2.

Deaths and immediately life-threatening SAEs will be reported within 1 business day after the site becomes aware of the event. All other SAEs will be reported within 3 business days of site awareness. SAEs will be reported either by fax or e-mail to all of the following:

- Sponsor: Office of Clinical Research Policy and Regulatory Operations, NIAID, NIH: Clinical Safety Office (CSO): [contact], [contact], [[contact]](mailto:[contact])
- DSMB Executive Secretary: [contact], [contact], [[contact]](mailto:[contact])
- LID, NIAID: [name], NIAID/NIH, [contact], [contact], Email: [[contact]](mailto:[contact])

SAEs will also be reported to WIRB (contact information below) based on its reporting requirements:

- Western Institutional Review Board (WIRB), [name], [contact]

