**Table 23: Pausing and Stopping Rules**

Specified Phase	Event	Reporting
Acute and Post-Acute Days 0 through 28 following inoculation for RSV-seropositive subjects and days 0 through 56 following inoculation for RSV-seronegative subjects	An SAE that cannot be attributed to an etiology or cannot be attributed to a cause unrelated to the study product.	A description of the vaccine-associated AE(s) or safety issue must be reported by the PI or study staff, within one business day of the PI's awareness, to the CSO and the DSMB by fax or email.
Acute Only Days 0 through 10 following inoculation for RSV-seropositive subjects and days 0 through 28 following inoculation for RSV-seronegative subjects	An LRI per Appendix IV , OR A fever of Grade 4 OR Any Grade 3 or above solicited AE (other than fever)	

The regulatory sponsor (OCRPRO) will determine if the FDA needs to be notified. The DSMB and regulatory sponsor will be informed and receive pertinent data of the event by the PI. Follow-up visits for participants already inoculated will continue as outlined in [Appendix II \(Table 30\)](#).

If the event is determined to have occurred in a participant who received active agent (vaccine), and the event meets one of the following stopping rule criteria, then the event will be reviewed by the DSMB prior to resuming enrollment.

1. One or more participants experience an SAE that cannot be attributed to an etiology or cannot be attributed to a cause unrelated to the study vaccine, OR
2. One or more participants develop LRI associated with shedding of vaccine virus at the time of the LRI (even if another pathogen is identified, unless the RSV is confirmed to be wt RSV), OR
3. One or more participants develop LRI that is not explained by a diagnosis unrelated to the vaccine virus, OR
4. One or more participants experiences a Grade 4 fever or any Grade 3 or Grade 4 solicited AE other than fever associated with shedding of vaccine virus, OR
5. Any pattern of research laboratory values or clinical symptoms is observed that the protocol team considers a significant safety issue for participants.

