## **9.2 OUTCOME MEASURES**

### **9.2.1 Primary Outcome Measures**

*Safety: Types and grades of study product-related:*

- Solicited AEs as defined in Appendix IV from Study Days 0-10 for RSV-seropositive and Study Days 0-28 for RSV-seronegative participants
- Unsolicited AEs from Study Days 0-10 for RSV-seropositive and Study Days 0-28 for RSV-seronegative participants
- SAE (Section 8.1.2) from Study Days 0-28 for RSV-seropositive and Study Days 0-56 for RSV-seronegative participants

*Infectivity:*

- Infection with RSV as defined as
  - 1) vaccine virus identified in a nasal wash from Study Days 0-10 for RSV-seropositive and Study Days 0-28 for RSV-seronegative (a binary outcome based on nasal washes done throughout the study period; Day 0 nasal wash will be counted as baseline); or
  - 2)  $\geq 4$ -fold rise in RSV neutralizing antibody titer from Study Days 0-28 for RSV-seropositive and Study Days 0-56 for RSV-seronegative subjects
- Peak titer of vaccine virus shed from Study Days 0-10 for RSV-seropositive and Study Days 0-28 for RSV-seronegative subjects
- Duration of virus shedding in nasal washes as determined by a) culture and b) RT-PCR from Study Days 0-10 for RSV-seropositive and Study Days 0-28 for RSV-seronegative subjects

*Immunogenicity:*

- $\geq 4$ -fold rise in RSV-neutralizing antibody titer from study entry to Study Day 28 for RSV-seropositive and from study entry to Study Day 56 for RSV-seronegative subjects
- $\geq 4$ -fold rise in IgG antibody responses to RSV F glycoprotein (ELISA) from study entry to Study Day 28 for RSV-seropositive and from study entry and Study Day 56 for RSV-seronegative subjects

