## **9.5 ANALYSES**

### **9.5.1 Assessment of Primary Objectives**

Safety data from all participants in CIR 322 who have been inoculated will be summarized together, including data from participants who discontinue study early or have some missed visits. In the immunogenicity analyses, those who do not provide data for the Day 28 Visit follow-up for RSV-seropositive participants and for the Day 56 Visit follow-up for RSV-seronegative participants (due to early discontinuation or missed visit) will be treated as “failures.” Sensitivity analyses will be performed to check if the results are consistent with those when these participants are excluded. Participants who receive any of the disallowed treatments listed in Section 5.10 during the first 28 days after inoculation for RSV-seropositive participants and during the first 56 days after inoculation for RSV-seronegative participants may be excluded from the immunogenicity evaluations after the time of the treatment. These participants, however, will be included in the safety evaluations for the duration of the study. These participants will not be replaced. Details of the analyses listed below will be included in the statistical analysis plan.

The frequency of solicited AEs and unsolicited AEs, along with 90% confidence intervals, during Study Days 0 to 10 in RSV-seropositive subjects and during Study Days 0 to 28 in RSV-seronegative subjects and of vaccine-related SAE during Study Days 0 to 28 in RSV-seropositive subjects and during Study Days 0 to 56 in RSV-seronegative subjects will be summarized. In addition, line listing of individual clinical solicited AEs and unsolicited AEs, graded by severity, will be prepared for events occurring during Study Days 0 to 10 in RSV-seropositive subjects and during Study Days 0 to 28 in RSV-seronegative subjects and vaccine-related SAE during Study Days 0 to 28 in RSV-seropositive subjects and during Study Days 0 to 56 in RSV-seronegative subjects.

The proportion of participants with infection defined as recovery of vaccine virus from a nasal wash as determined by culture and RT-PCR, and/or a  $\geq 4$ -fold rise in neutralizing antibody titer to RSV, will be summarized. A line listing of the individual peak titer of vaccine virus shed and duration of virus shedding in nasal washes by each individual will be prepared. In addition, the geometric mean peak titer and mean duration of virus shed will be provided for each treatment group.

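### A non-serious Group 1 LRI on Days 11-28 is recorded and can block progression to Group 2, but no specified outcome, summary or listing is required to show it

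*Combined protocol and SAP*

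**What the plan says.** **Progression.** The paragraph under Table 1 in the Protocol Summary opens Group 2 only if Group 1 has at most two vaccine-associated solicited AEs, counted on Days 0-10, and "no vaccine-associated lower respiratory illnesses (LRIs) (Days 0 through 28) in RSV-seropositive children". LRI therefore has its own, longer window there. Section 3 restates the rule as "no vaccine-associated LRIs in RSV-seropositive children", with no days given.

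**Recording.** For Group 1 on Days 11-28, Table 19 requires "All LRIs and SAEs" on the CRF. The corresponding post-acute row for Group 2 in Table 20 lists SAEs only.

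**Classification.** Section 8.1.1 and Appendix IV list LRI among the solicited AEs.

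**Outcome and analysis.** Objective 1 in Section 2.1 covers "solicited and unsolicited AEs in RSV-seropositive participants (group 1) from day 0 through the 10th day following inoculation". Section 9.2.1 has "Solicited AEs as defined in Appendix IV from Study Days 0-10 for RSV-seropositive and Study Days 0-28 for RSV-seronegative participants". Section 9.5.1 plans "The frequency of solicited AEs and unsolicited AEs, along with 90% confidence intervals, during Study Days 0 to 10 in RSV-seropositive subjects", and its line listing of solicited and unsolicited AEs has the same limit. Product-related SAEs are the exception: in all three sections they run to Day 28 in Group 1.

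**Other rules that use LRI.** In Table 23 an LRI triggers a pause in the acute phase only, "Days 0 through 10 following inoculation for RSV-seropositive subjects". Section 7.3 requires expedited reporting of "LRIs as defined in Appendix IV if they occur during study days 0 to 10 in groups 1".

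**The concern.** The plan handles one kind of event in one group under two windows. For recording and for the Protocol Summary's progression decision, Group 1 LRI counts to Day 28. As an outcome, a frequency with a confidence interval and a line listing, it ends at Day 10 unless it is also a product-related SAE.

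Suppose a vaccinee has a non-serious, vaccine-associated LRI starting on Day 12. It goes on the CRF and, under the Protocol Summary, Group 2 does not open. An analyst who follows Section 9.5.1 to the letter then reports no LRI among Group 1 vaccinees if none occurred by Day 10. The published safety table would not show why the trial did not progress. LRI is the event on which Section 9.3.1 centres its tolerability calculations, so this is a poor place for the report and the decision to rest on different data.

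**Working it through.** **1. The windows side by side (Group 1, LRI that is not a product-related SAE)**

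| Use of the event | Source | Window |
|---|---|---|
| Progression to Group 2 | Protocol Summary, under Table 1 | Days 0-28 |
| Progression, restated | Section 3 | none stated |
| CRF recording | Table 19 | Days 0-10 as a solicited AE; Days 11-28 as an LRI |
| Primary objective 1 | Section 2.1 | Days 0-10 |
| Primary outcome | Section 9.2.1 | Days 0-10 |
| Frequency with 90% CI; line listing | Section 9.5.1 | Days 0-10 |
| Pause trigger | Table 23 | Days 0-10 |
| Expedited reporting | Section 7.3 | Days 0-10 |

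Days 0-28 are 29 days and Days 11-28 are 18 of them: 18/29 = 62% of the progression window lies outside the outcome window. That is a share of days, not of risk.

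**2. The plan's own intervals.** Table 25 gives exact 90% CIs for N = 10. They reproduce with Clopper-Pearson limits:
- 0/10: upper limit 1 - 0.05^(1/10) = 0.259, so 0-26%, as printed.
- 1/10: beta quantiles give 0.005 to 0.394, so 1-39%, as printed.

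With 10 vaccinees in Group 1 (Table 1), one LRI on Days 11-28 and none before is reported as 0/10 (0-26%) under the Day 10 limit and as 1/10 (1-39%) under a Day 28 limit.

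**3. How often this could happen.** The documents give no LRI rate for seropositive vaccinees, so the inputs are assumptions. Let p be a vaccinee's LRI risk over Days 0-28 and q the share of that risk after Day 10. With n = 10 independent vaccinees and every event captured,

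P(at least one LRI by Day 28, none by Day 10) = [1 - p(1 - q)]^10 - (1 - p)^10.

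| p | q = 0.62 | q = 0.35 | q = 0.20 |
|---|---|---|---|
| 1% | 0.963 - 0.904 = 0.06 | 0.937 - 0.904 = 0.03 | 0.923 - 0.904 = 0.02 |
| 3% | 0.892 - 0.737 = 0.15 | 0.821 - 0.737 = 0.08 | 0.784 - 0.737 = 0.05 |
| 10% | 0.679 - 0.349 = 0.33 | 0.511 - 0.349 = 0.16 | 0.434 - 0.349 = 0.09 |

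The value q = 0.62 corresponds to risk spread evenly over the 29 days.

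**4. Direction of error.** These probabilities are too high for the gap as defined here, for three reasons. They count LRIs that are product-related SAEs, which are reported. They count LRIs that are not vaccine-associated, which do not block progression. They also assume full capture, whereas after Day 10 parents are told to call about possible SAEs (Section 6.5.1.4), and the Day 28 history asks for provider visits and for illness that meets SAE criteria (Table 8).

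**The case against.** The other side has several fair points.

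- **SAEs are covered.** A reader might infer that the whole Group 1 safety analysis ends at Day 10. It does not: a product-related LRI that meets an SAE criterion, such as hospitalization, is an objective, an outcome and a listed event through Day 28. This stands, and it limits the point to the remaining LRIs.
- **The event need not vanish.** A reader might also infer that such an LRI could appear nowhere. Section 9.5.1 opens by saying that safety data from all inoculated participants will be summarized, and it leaves detail to the statistical analysis plan. Section 9.4.2 sends LRIs to the DSMB. The first statement sets the population and permits a Day 11-28 LRI summary without requiring one, and the specific sentences that follow it stop at Day 10. DSMB reporting is monitoring, not the trial's reported result.
- **Different windows can be deliberate.** A cautious progression rule may look further ahead than the outcome, and scheduled Group 1 nasal washes for virus end at Day 10, so later LRIs are harder to attribute. A result labelled Days 0-10 and a decision labelled Days 0-28 can both be true, so this is not a formal contradiction. It remains a reporting gap, because nothing specified connects the two.
- **The Day 28 limit is not settled.** It stands in the Protocol Summary but not in Section 3. This is correct, and it is a reason to reconcile the text.
- **Pausing, expedited reporting and progression are separate mechanisms.** They may have different windows. The plan should then say that the difference is intended.
- **LRI is rare.** Section 9.3.1 says so, and Section 3 reports strong restriction of earlier vaccines of this type in children with titers of 1:40 or more. The 10% row should therefore not be read as an estimate.

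**Conclusion.** The concern holds in this form: a Group 1 LRI with onset on Days 11-28 that is not a product-related SAE is recorded and, if vaccine-associated, blocks Group 2 under the Protocol Summary, while no specified outcome, frequency or listing has to include it. This rests on comparing the text of the sections and needs no assumed rate.

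The effect of one event is exact: 0/10 against 1/10 vaccinees. Its probability is not known. Under the stated assumptions it lies between about 2% and 33%, and at the 1% and 3% risks, which fit the plan's own description of LRI better, between about 2% and 15%. It falls further if non-serious LRIs go undetected.

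The study is exploratory and Group 1 is small, so this does not threaten its design. It is still worth correcting, because the missing event would be the one that explains a progression decision.

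**What to change.** **Analysis.** In Sections 2.1 (objective 1), 9.2.1 and 9.5.1, keep Days 0-10 for the other Group 1 solicited AEs and for unsolicited AEs. For LRI, add frequency with 90% CI and a line listing for Days 0-28, by arm, next to the Days 0-10 figure. Section 9.5.1 already uses a Day 28 limit for SAEs, and Table 19 already puts the data on the CRF.

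**Reconciliation.** The sponsor should reconcile the Group 1 LRI windows in the Protocol Summary (Days 0-28), Section 3 (none stated), Table 23 (Days 0-10) and Section 7.3 (Days 0-10), or state that they differ on purpose. Which window applies to progression, pausing or expedited reporting is not for this review.

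**Cost.** Wording changes in three sections, one extra summary row and a longer listing. No additional data collection is needed to report what Table 19 already requires. The Group 1 LRI rate may look less favourable, and because Days 11-28 are followed less closely than Days 0-10, the longer-window figure should carry a note on ascertainment.
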